9.4.7 Serious Adverse Events

A Serious Adverse Event (SAE) is defined as any untoward medical occurrence that, at any dose,

- Results in death
- Is immediately life-threatening (i.e., in the opinion of the Investigator, the AE places the subject at immediate risk of death; it does not include a reaction that, had it occurred in a more severe form, might have caused death)
- Requires inpatient hospitalization or results in prolongation of an existing hospitalization

- Results in persistent or significant disability or incapacity
- Is a congenital anomaly or birth defect
- Is an important medical event that may not be immediately life-threatening, result in death, or require hospitalization, but may be considered an SAE when, based upon appropriate medical judgment, it jeopardizes the subject or may require medical or surgical intervention to prevent one of the outcomes listed above

As soon as the Investigator becomes aware of an AE that meets the criteria for an SAE, the SAE should be documented to the extent that information is available. A report must be submitted by the study site to the Sponsor or designee within 24 hours.

Any SAE, regardless of causal relationship, must be reported to the Sponsor immediately (within 24 hours of the Investigator's knowledge of the event).

SAEs will be recorded from the time of informed consent/assent, through to end of the study. If, in the opinion of the Investigator, an SAE occurring outside the specified time window, (i.e., following subject completion or terminations of the study) is deemed to be drug-related, then the event should be reported with 24 hours as outlined above.

The Investigator should institute any clinically necessary supplementary investigation of SAE information. In the case of subject death, any post-mortem findings/reports will be requested.

9.4.7.1 Reporting of Serious Adverse Events

All SAEs, as defined by the criteria above, must be reported to the Sponsor or designee using the SAE form provided, within 24 hours of the Investigator becoming aware of the event.

Serious adverse events must be recorded on an SAE form. The minimum information required for SAE reporting includes the identity of the PI, site number, subject number, event description, SAE term(s), reason why the event is considered to be serious (i.e., the seriousness criteria), and PI's assessment of the relationship of the event to study drug. Additional SAE information including medications or other therapeutic measures used to treat the event, and the outcome/resolution of the event should also be recorded on the SAE form.

In all cases, the Investigator should continue to monitor the clinical situation and report all material facts relating to the progression or outcome of the SAE. The Investigator may be required to provide supplementary information as requested by the Sponsor or its designee.

When reporting SAEs, the following additional points should be considered:

- When the diagnosis of an SAE is known or suspected, the Investigator should report the diagnosis or syndrome as the primary SAE term, rather than as signs or symptoms; signs, symptoms and tests that support the diagnosis should be provided
- Death should not be reported as an SAE, but as an outcome of a specific SAE, unless the event preceding the death is unknown. If an autopsy was performed, the autopsy report should be provided;

While most hospitalizations necessitate reporting of an SAE, some hospitalizations do not require SAE reporting, as follows:

- Hospitalization for elective or previously scheduled surgery or procedure for a preexisting condition that has not worsened after administration of study drug (e.g., a previously scheduled ventral hernia repair). SAEs must, however, be reported for any surgical or procedural complication resulting in prolongation of the hospitalization;
- Events that result in hospital stays for observation only of fewer than 24 hours and that do not require a therapeutic intervention/treatment (e.g., an emergency room visit for hematuria that results in a diagnosis of cystitis and discharge to home on oral antibiotics).

The Sponsor will process and evaluate all SAEs as soon as the reports are received. For each SAE received, the Sponsor will make a determination as to whether the criteria for expedited reporting to relevant regulatory authorities have been met.

The Sponsor will assess the expectedness of each SAE to the study treatment. The current Investigator's Brochure will be used as the reference document to assessed expectedness of the event to study drug.

9.4.8 Dosing Changes due to AEs

Dose interruptions are allowed should a subject experience intolerable treatment-related adverse events (e.g., pruritis) on study. In cases where the Investigator feels a dose interruption is warranted, the subject should be instructed to interrupt study drug application to allow symptoms to resolve. Subjects should be instructed to return to the twice daily application regimen within 2 days of dose interruption.

Dosing interruptions are to be recorded in the subject diary as a missed dose.

Study drug must be discontinued if an adverse event is deemed persistent and if continuation of study drug would not be in the best interest of the subject.

Refer to Section 10.3 for further information regarding discontinuation of study drug or early withdrawal

9.4.9 Pregnancy

Should a subject become pregnant during study participation, study drug dosing will be discontinued and the subject will be withdrawn from study. The Investigator must perform medical assessments as clinically indicated and continue to follow the subject for at least 4 weeks after delivery. Details for both the mother and baby must be obtained. Pregnancy is not itself an AE or SAE; however, maternal/fetal complications or abnormalities will be recorded as AEs or SAEs, as appropriate. The Investigator must complete a study-specific pregnancy form upon confirmation of a pregnancy. Pregnancy reporting forms will be provided to the study site.

10 STUDY DISCONTINUATIONS

10.1 Discontinuation of the Study

The Sponsor has the right to terminate or to stop the study at any time. Should this be necessary, both the Sponsor and the Investigator will ensure that proper study discontinuation procedures are completed. The entire study will be stopped if:

- Evidence has emerged that, in the collective opinion of the Investigators at each site with the concurrence of the Sponsor or the sole opinion of the Sponsor, makes the continuation of the study unnecessary or unethical
- The stated objectives of the study are achieved
- The Sponsor discontinues the development of the study drug

Regardless of the reason for withdrawal, all data available for the subject at the time of discontinuation of follow-up must be recorded in the eCRF. All reasons for discontinuation of treatment must be documented.

10.2 Early Study Termination of Study Subjects

The Investigator will make every reasonable effort to keep each subject in the study; however, a subject may voluntarily withdraw from study participation at any time. If the subject withdraws consent and discontinues from the study, the Investigator will attempt to schedule an Early Termination visit as soon as possible, determine the reason for discontinuation, and record the reason in the subject's study records and in the eCRF.

If at any time during the study, the Investigator determines that it is not in the best interest of the subject to continue, the subject will be discontinued from participation. The Investigator can discontinue a subject at any time if medically necessary. The Investigator may discontinue a subject's participation if the subject has failed to follow study procedures or to keep follow-up appointments. Appropriate documentation in the subject's study record and eCRF regarding the reason for discontinuation must be completed.

All subjects who fail to return to the study site for the required follow-up visits will be contacted by phone to determine the cause(s) why the subject failed to return for the necessary visit or elected to discontinue from the study. If a subject is unreachable by telephone after a minimum of two documented attempts (one attempt on two different days), a registered letter will be sent requesting that subject contact the site regarding study follow-up.

Subjects will be discontinued early from the study if any of the following occur:

- Withdrawal of informed consent (subject's decision to withdraw for any reason)
- Any clinical adverse event, laboratory abnormality, or inter-current illness which, in the opinion of the Investigator, indicates that continued treatment and/or participation in the study is not in the best interest of the subject
- Death

- Serious protocol violation, including persistent noncompliance or subject requiring medication or procedures prohibited by the protocol, to allow subjects to receive the appropriate medical attention.
- Discontinuation of the study by the Sponsor

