10.3 Study Drug Discontinuation

For subjects who decide to prematurely discontinue study drug treatment, all reasonable efforts should be made to obtain all protocol-specified safety assessments and end of study procedures.

The Investigator should stop study drug treatment in the following instances:

- Inter-current illness that would, in the judgment of the Investigator, affect assessments of clinical status to a significant degree.
- Any clinical adverse event which is clinically significant and is deemed persistent and probably or definitely related to study drug in the judgment of the Investigator.
- Unacceptable toxicity

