7.3 Handling of Dropouts or Missing Data

Missing 12 week efficacy data will be imputed and subsequently analyzed. The primary method of handling missing efficacy data will be the method of MCMC multiple imputation which does not rely on the assumption of data missing at random. Additionally, the pattern of missing observations in each treatment group will not influence the missing value estimation in the other because the imputation will be conducted independently for each treatment group.

The multiple imputation process for imputing missing lesion count and IGA data and subsequent analysis will involve 4 distinct phases with these principal tasks:

- 1. Calculate the number of missing 12-week values for each treatment group to be estimated by MCMC. Let nmiss be the maximum number of missing between the two treatment groups.
- 2. Create a data set of subjects, one for each treatment group, with observed values and those needing estimation by MCMC. The missing values in each data set will be filled in using the MCMC method '5 x nmiss' times to generate '5 x nmiss' data sets. The resulting data sets for each treatment arm will be combined into one complete data set for each imputation.
- 3. For each complete data set, compute the necessary derived variables. Each complete data set will be analyzed with the appropriate analysis model. See Sections 7.3.1.1 and 7.3.1.2 for details.
- 4. The results from these analyses will be combined into a single inference using SAS PROC MIANALYZE.

Sensitivity analyses will be performed on the primary efficacy endpoints to investigate the impact of the method of imputation. The first set of sensitivity analyses will use repeated measures. See Sections 7.3.2.1 and 7.3.2.2 for details.

The second set of sensitivity analyses will use model-based multiple imputation. The model-based multiple imputation process requires the data to have a monotone missing pattern. However, the imputation model will include treatment group and analysis center, and for lesion counts will include a covariate of baseline lesion count. Since treatment group, analysis center and baseline lesion count will be non-missing, the data will have a monotone missing pattern. The model-based multiple imputation process will involve 4 principal tasks:

- 1. Calculate the number of missing 12-week values to be imputed (nmiss).

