7.9 Statistical Analysis

All analyses will be performed by QST. All summary tables and data listings will be prepared utilizing SAS® software. The standard operating procedures of QST will be followed in the creation and quality control of all data displays and analyses.

All data collected at scheduled time points will be summarized, regardless of treatment with study drug. Post-treatment assessments for subjects who discontinue treatment but continued to be followed in the study will be included in summaries.

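### Protocol 10.2 ends study participation, not only study drug, after a serious protocol violation, so obtainable Week 12 outcomes can be lost, with a bias of unknown size and direction

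*Protocol*

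**What the plan says.** **Leaving the study.** Protocol 10.2 first asks the investigator to try to retain every subject. It then gives a mandatory list: "Subjects will be discontinued early from the study if any of the following occur". One entry is "Serious protocol violation, including persistent noncompliance or subject requiring medication or procedures prohibited by the protocol"; the reason given is access to medical care. The adverse-event entry covers events after which further treatment, further participation, or both would not serve the subject. A discretionary route also exists: "The Investigator may discontinue a subject's participation if the subject has failed to follow study procedures or to keep follow-up appointments".

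**Early termination visit.** The instruction in 10.2 is tied to consent withdrawal: "If the subject withdraws consent and discontinues from the study, the Investigator will attempt to schedule an Early Termination visit as soon as possible". Protocol 8.7 and Appendix 1 combine this visit with Week 12 and include IGA and lesion counts. SAP 7.9.2 assigns an early termination or unscheduled visit to Week 12 only on study days 71 to 98.

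**Stopping drug.** Protocol 10.3 is separate: "For subjects who decide to prematurely discontinue study drug treatment, all reasonable efforts should be made to obtain all protocol-specified safety assessments", and it extends this effort to end-of-study procedures.

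**Analysis.** SAP 7.9 says: "Post-treatment assessments for subjects who discontinue treatment but continued to be followed in the study will be included in summaries". The ITT population (SAP 7.8.2) holds everyone randomized and dispensed drug. For missing Week 12 values, SAP 7.3 says "the imputation will be conducted independently for each treatment group". The code in Protocol 11.7 lists baseline, Week 4, Week 8 and Week 12 as the only variables. Both documents say that the method does not depend on data being missing at random.

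**The concern.** Section 10.2 treats a reason to stop study drug, or to use another treatment, as a reason to stop measuring the outcome. The prohibited list in Protocol 7.2 includes benzoyl peroxide, topical and oral retinoids and systemic anti-acne drugs. A subject whose acne is not responding might well seek these, and one who cannot tolerate the gel may stop applying it. Removal by this route is therefore plausibly related to outcome.

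Removed subjects stay in the ITT analysis of all three co-primary variables. Their Week 12 values come from a model fitted within arm that knows only the earlier scores. It does not know that the subject stopped applying the product, why the subject left, or whether another treatment was started. If those facts predict Week 12 beyond the earlier scores, the imputed values are biased. No later analysis can recover an outcome that was never collected.

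**Working it through.** **1. The plan's own figures** (Protocol 11.14, SAP 4.2)

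- IGA, 20.5% against 9.6%, 2:1 allocation (k = 2), pooled rate (0.096 + 2 × 0.205)/3 = 0.1687. Uncorrected vehicle n = [1.960 × √(0.1687 × 0.8313 × 1.5) + 1.645 × √(0.096 × 0.904 + 0.205 × 0.795/2)]² / 0.109² = 208.4. Continuity correction: (208.4/4) × [1 + √(1 + 3/(208.4 × 0.109))]² = 222.0. This matches 222 vehicle and 444 active at 95% power.
- Non-inflammatory: 5.03/[16.72 × √(1/450 + 1/225)] = 3.68, power Φ(3.68 − 1.96) = 95.8% (stated 95%).
- Inflammatory: 5.51/[11.00 × √(1/300 + 1/150)] = 5.01, power 99.9% (stated at least 95%).
- No dropout rate is stated. The margin implied by 700 subjects is 1 − 675/700 = 3.6% for non-inflammatory lesions and 1 − 666/700 = 4.9% for IGA.

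**2. Power is not the issue.** Starting from 467 + 233, a 20% loss in both arms carrying no information about outcome leaves 90.4% power for IGA and 91.8% for non-inflammatory lesions, each taken singly.

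**3. Which values are lost.** By SAP 7.9.2, an early termination visit on days 19–42 maps to Week 4 and on days 43–70 to Week 8, and is used only if that scheduled visit has no data. Only days 71–98 supply Week 12. A subject removed and last seen before day 71 has no Week 12 value.

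**4. Bias, vehicle-like scenario (assumed).** A share m of each arm is removed, with m = 5%, 10% or 15% because the documents give no rate. Those who stay follow the planning figures, removed subjects truly have the vehicle outcome, and Weeks 4 and 8 carry no information. The reported difference is then D and the true difference is (1 − m) × D, so the overstatement is m × D.

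| Variable | D | m = 5% | m = 10% | m = 15% |
|---|---|---|---|---|
| IGA (percentage points) | 10.9 | 0.5 | 1.1 | 1.6 |
| Non-inflammatory lesions | 5.03 | 0.25 | 0.50 | 0.75 |
| Inflammatory lesions | 5.51 | 0.28 | 0.55 | 0.83 |

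These are upper bounds for this scenario, because the primary imputation does use Weeks 4 and 8. As an illustration, suppose removed subjects already show the full 5.03-lesion deficit at Week 8 and the Week 8 to Week 12 slope is 0.5 to 0.8 (assumed). The 0.50-lesion bias then falls to 0.50 × (1 − slope) = 0.25 to 0.10.

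**5. Direction, no-response scenario (assumed).** Removed subjects in both arms truly have no success and no lesion change, but are imputed like those who stay. The true IGA difference is (1 − m_active) × 20.5 − (1 − m_vehicle) × 9.6, against 10.9 reported.

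| Removed, active / vehicle | True IGA difference | Reported minus true |
|---|---|---|
| 10% / 10% | 9.8 | +1.1 |
| 15% / 5% | 8.3 | +2.6 |
| 5% / 10% | 10.8 | +0.1 |
| 5% / 15% | 11.3 | −0.4 |

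The IGA bias changes sign when the vehicle share exceeds 20.5/9.6 = 2.1 times the active share. For non-inflammatory lesions the ratio is 14.73/9.70 = 1.5, and for inflammatory lesions 15.21/9.7 = 1.6.

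**6. Sensitivity analyses** (SAP 7.3.2). The first is a repeated-measures model on observed data. The second imputes from the analysis model: treatment and center, plus baseline count for lesions. Neither shifts the imputed values of subjects who leave. The second does not use Weeks 4 and 8, so it comes closer to the bounds in step 4 than the primary analysis does. Imputing by arm does not remove the missing-at-random assumption of the specified MCMC method, despite what both documents say.

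**The case against.** The strongest reply is that the route is narrow and partly repaired.

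- The trigger is a serious violation, with noncompliance that is persistent. Protocol 6.6 has deviating subjects counseled, and 7.2 allows systemic antibiotics for acute infection. The per-protocol exclusions for noncompliance and interfering medication suggest that some such subjects do reach Week 12. This stands: 5–15% is an assumption, and the plan's implied margin for all dropout is below 5%.
- A reader might infer that removal always loses Week 12. It does not, since an early termination visit on days 71–98 counts. Earlier removals do lose it, and 10.2 does not direct such a visit for subjects removed for a violation.
- A reader might infer that removed active subjects are imputed at completer levels, so that the error must favor the drug. The documents do not support this. Imputation conditions on the subject's own earlier scores, and vehicle removals may also be worse than their arm's average.
- A reader might infer that SAP 7.9 already accepts Week 12 values obtained after prohibited acne therapy. Its text concerns being on or off study drug. How values after other treatment enter the primary analysis is a choice the documents have not made.
- A reader might see a flat contradiction between 10.2, 10.3 and SAP 7.9. They can be read together: 10.2 governs leaving the study, 10.3 stopping drug, and SAP 7.9 those still followed. What remains is a gap. The 10.3 effort is worded for subjects who themselves decide to stop, and the adverse-event entry in 10.2 blurs the two states that the SAP keeps apart.

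**Conclusion.** The point holds as a retention weakness. Section 10.2 makes study-level removal mandatory for these violations, the 10.3 effort does not clearly reach those subjects, and the analysis plan has no means of testing whether their missing Week 12 values differ from what the model predicts.

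The size and direction of any bias are unknown, because no removal rate by arm is given. The 0.5–1.6 IGA points and 0.25–0.8 lesions are ceilings for one assumed scenario: 5–15% removed per arm, vehicle-like outcomes and uninformative earlier visits. They are not a limit on every scenario. With no response among those removed and 15% active against 5% vehicle lost, the IGA overstatement is 2.6 points; with 5% against 15% it becomes an understatement of 0.4. The planned sample size and power are unaffected. This supports an inexpensive improvement, not a claim that the planned result would be invalid or would favor the active gel.

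**What to change.** Reconcile Protocol 10.2 with 10.3 and SAP 7.9 by distinguishing discontinuation of study drug from discontinuation of follow-up.

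- Leave every rule on when drug is stopped and what care is given as it is. Section 10.3's list for stopping drug names neither noncompliance nor prohibited medication, so the sponsor must make drug status explicit for these subjects when the sections are aligned. This point takes no position on it.
- Unless consent is withdrawn, seek the scheduled Week 12 IGA and lesion counts from subjects now removed under 10.2. Record any other acne treatment and its dates.
- Include values obtained off study drug in the ITT analysis, as SAP 7.9 foresees. State before unblinding how values after prohibited acne therapy are handled.
- For values still missing, correct the statement about missing at random and add a sensitivity analysis that shifts the imputed values, such as a tipping-point analysis.

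**Cost:** protocol and SAP wording and a few visits already on the schedule, with no change to 467 + 233. The downside is that some Week 12 values will reflect other treatment, which is why their handling has to be stated in advance.

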10.3 Study Drug Discontinuation

For subjects who decide to prematurely discontinue study drug treatment, all reasonable efforts should be made to obtain all protocol-specified safety assessments and end of study procedures.

The Investigator should stop study drug treatment in the following instances:

- Inter-current illness that would, in the judgment of the Investigator, affect assessments of clinical status to a significant degree.
- Any clinical adverse event which is clinically significant and is deemed persistent and probably or definitely related to study drug in the judgment of the Investigator.
- Unacceptable toxicity

11 STATISTICAL CONSIDERATIONS

11.1 General Statistical Methodology

All statistical processing will be performed using SAS® unless otherwise stated. No interim analyses are planned. Except where noted, all statistical tests will be two-sided and will be performed at the 0.05 level of significance.

Descriptive statistics will be used to provide an overview of the efficacy and safety results. For categorical parameters, the number and percentage of subjects in each category will be presented. For continuous parameters, descriptive statistics will include n (number of subjects), mean, standard deviation (SD), median, minimum and maximum. Appropriate inferential statistics will be used for the primary, secondary, and exploratory efficacy variables.

The primary method of handling missing efficacy data will be the method of Markov Chain Monte Carlo (MCMC) multiple imputation.

Demographic data will be summarized by treatment group using descriptive statistics. Subjects' baseline characteristics related to efficacy analyses will be compared between treatment groups to evaluate baseline balance between the treatment arms.

The number of subjects in each analysis set will be summarized. Reasons for study withdrawal during the blinded study will be summarized using frequencies and percentages by treatment group.

The primary method of dichotomizing the IGA score will be to consider a subject a "success" if the IGA at a post-baseline visit is 0 or 1 and 2 or more grades lower than at baseline; otherwise the subject will be considered a treatment "failure".

A statistical analysis plan (SAP), describing all statistical analyses will be provided as a separate document. The SAP will be finalized prior to unblinding of the study treatments.

